## Sponsor

High Flow Nasal Cannula Devices will be donated by Fisher & Paykel Healthcare, Inc.

## Introduction and Background

Over the last few years, High Flow Nasal Cannula (HFNC) has been gaining a lot of popularity in adult population. High Flow Nasal Cannula oxygen therapy consist of an air/oxygen blender, an active humidifier, a single heated circuit, and a nasal cannula. It has the potential to deliver a flow rate up to 60L/min in adults and an inspiratory fraction of oxygen (FiO2) close to 100%. Multiple mechanisms have been suggested to contribute to the clinical benefit of HFNC, including and not limited to:

- The use of small loose-fitting nasal prongs leads to enhanced patient comfort
- Heat and humidification increase water content of mucus, facilitating secretions removal, minimizing desiccation/epithelial injury, and decreasing metabolic cost/work of breathing;
- Higher nasal flow rate provides a more reliable FiO2 delivery by reducing inspiratory entrainment of room air
- Washout of upper airway dead space improves efficiency of ventilation and enhances oxygen delivery
- Generation of a positive end-expiratory pressure (PEEP) counterbalances auto-PEEP and decreases work of breathing

The use of HFNC has been limited to the inpatient setting, and mostly to intermediate care (step down) and intensive care units. It has been predominantly used in mild to moderate hypoxemic respiratory failure to delay and hopefully prevent endotracheal intubation and mechanical ventilation. A recent large, randomized, multicenter trial showed that in hypoxemic non-hypercapnic respiratory failure, HFNC has similar intubation rate to non-invasive positive pressure ventilation (NIPPV), but a lower 90 days mortality. On the other hand, the data on

HFNC use in other settings is lacking and is limited to anecdotal cases and small pilot studies. Despite this lack of strong data, HFNC has been frequently used in a variety of patients with different diseases. It has been used in acute pulmonary edema, in immunocompromised and Do-Not-Intubate patients, pre-intubation, post-extubation, during endoscopy, in sleep apnea, and even in acute COPD exacerbation.

Data on HFNC use in patients with COPD include the following:

- In a small recent study including patients with stable COPD and moderate hypercapnia (PaCO2 ~ 53mmHg), six weeks of HFNC caused a significant drop in PaCO2 (~ 8 mmHg), comparable to the drop observed with NIPPV.
- A small pilot study looked into effects of eight hours of HFNC on ventilation in healthy volunteers, COPD, and idiopathic pulmonary fibrosis patients. In patients with stable COPD, an increase in tidal volume (VT) was noted with a drop in PaCO2, despite a drop in respiratory rate (RR) and minute ventilation (MV).
- In another small pilot study, 45 min of HFNC at 20L/min on RA, lead as well to a decrease in respiratory rate and no significant change in PaCO2.

This suggests that HFNC increases the efficiency of breathing/ventilation. HFNC generates low levels of positive end-expiratory pressure (PEEP) which is known to decrease ventilation/perfusion mismatch. Low levels of PEEP may contribute as well to alveolar recruitment and decrease dead space/tidal volume (VD/VT) ratio. Through delivering a higher flow, HFNC may be contributing to the washout of upper airway dead space as well.

Based on the proposed mechanism of actions, the physiologic effects of HFNC (loosening up secretions, washing out dead space, and generating a CPAP/PEEP effect), and the data from previous pilot studies showing an improvement in respiratory efficiency with HFNC; we postulate that the use of HFNC in patients with stable COPD in the outpatient setting is safe, and may result in BCSS score reduction, better quality of life, and possibly fewer exacerbations.

What distinguishes our study is, that to the best of our knowledge, it is the first one where HFNC effectiveness will be studied in COPD patients in the outpatient setting, and for a relatively longer period of time. A positive outcome may open the door for a larger randomized controlled study, which if it validates this outcome, may provide patients with COPD an effective non-invasive alternative home device.

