## **Objectives**

The primary objective of this study is to look for a correlation between the use of HFNC in the outpatient setting in patients with previous COPD exacerbation and the change in their BCSS score. We hypothesize that home use of HFNC will lead to a reduction in BCSS score by 1.3.

Secondary objectives include; looking for a correlation between the use of home HFNC and COPD exacerbations in a 6 month period. COPD exacerbations are defined as worsening symptoms of COPD requiring a change in baseline medications/inhalers or a steroid or antibiotic prescription. No arterial blood gases will be performed as part of the study but we will look for PaCO2/serum bicarbonate change with the use of home HFNC, when possible.

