After 3-4 months follow-up post enrollment, patients will be brought to the clinic for HFNC education/fitting. A baseline BCSS score (BCSS0) will be completed and the mean of last 3 months' BCSS scores ( $\overline{BCSS}_{w/oHFNC}$ ) will be calculated. The number of COPD exacerbation per last 3 months with new baseline PaCO2/serum bicarbonate, if available, will be collected. The HFNC device will be set at a fixed flow of 30L/min and a FiO2 of 21% (room air). Patients will be instructed to wear HFNC as long as they can while targeting at least 6 hours/day, and to record the number of hours they wear it per day. Patients will continue to complete the BCSS score every night or at least 3 times per week. After 6-8 weeks, a follow-up appointment over the phone or in the clinic will take place.

At the end of the 3 months HFNC trial, patients will be brought back to the clinic, and a BCSS score will be completed (BCSS3) and the mean BCSS of the last 3 months ( $\overline{BCSS}_{w/HFNC}$ ) will be calculated. The number of hours/day wearing the HFNC, the number of COPD exacerbations per last 3 months, and new baseline PaCO2/serum bicarbonate (if available), will be collected.

Both the difference between the mean of baseline BCSS scores ( $\overline{BCSS}_0$ ) and the mean of BCSS scores post 3 months HFNC ( $\overline{BCSS}_3$ ), ( $\Delta 0-3 \overline{BCSS}$ ); and the difference between the means of BCSS without HFNC ( $\mu_{\overline{BCSS}_{w/oHFNC}}$ ) and with HFNC ( $\mu_{\overline{BCSS}_{w/HFNC}}$ ), ( $\Delta \mu_{\overline{BCSS}_{w/oHFNC}} - \mu_{\overline{BCSS}_{w/HFNC}}$ ) will be calculated. The difference between the means of number of COPD

exacerbation per 3 months pre and post-HFNC, and the means of baseline PaCO2/serum bicarbonate (if available) pre and post-HFNC will be calculated as well, as secondary objectives. We will also look for a possible correlation between the number of hours using home HFNC and the change in BCSS score.

Regardless of the change/or not in BCSS score, patients will be able to provide their feedback regarding the device; they will be asked how helpful it was on a scale of 0 to 3, with 0 being equivalent to “not helpful at all” and 3 corresponding to “very helpful”. Patients will be asked as well if they would like to keep/not keep the device.

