### **Risks and Side Effects:**

No major risks or side effects are expected during the study since no invasive interventions will be performed. Infrequently, patients may develop a localized facial trauma and erythema at pressure areas, discomfort, and epistaxis.

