### **Data management and Safety Monitoring Plan**

All the data will be recorded anonymously using study subject number rather than personal identifiers. There will be one password protected master list kept on an encrypted computer with patient’s name and DOB correlating with study subject number. This computer will be secured in a locked office in the section of pulmonary and critical care office.

OUHSC regulations regarding electronic information and data security will be followed. If an incident such as loss or theft of data or storage media, unauthorized access of sensitive data or devices, or non-compliance with security controls occurs, the PI will be notified and will report the data security incident to OUHSC authorities.

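### The plan postulates that home HFNC is safe and names device-related harms, but plans no systematic recording of those harms, of serious events or of reasons for stopping.

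*Combined protocol and SAP*

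**What the plan says.** The rationale that closes the Introduction and Background reads: "we postulate that the use of HFNC in patients with stable COPD in the outpatient setting is safe". The expected benefits follow in more tentative terms. Safety does not reappear in the Objectives. The primary hypothesis there is "We hypothesize that home use of HFNC will lead to a reduction in BCSS score by 1.3", and the secondary aim is "looking for a correlation between the use of home HFNC and COPD exacerbations in a 6 month period". PaCO2 and bicarbonate are compared only where values happen to exist, since "No arterial blood gases will be performed as part of the study".

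Study Design and Methodology collects demographics, FEV1 and a diary BCSS. At the end of the HFNC period it adds "The number of hours/day wearing the HFNC, the number of COPD exacerbations per last 3 months, and new baseline" PaCO2 or bicarbonate if available. Patients also rate the device's helpfulness from 0 to 3 and say whether they would keep it. A phone or clinic contact falls at 6-8 weeks in each period. The one before HFNC is meant to improve compliance, and no content is given for the one on HFNC.

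Risks and Side Effects expects no major risk but adds: "Infrequently, patients may develop a localized facial trauma and erythema at pressure areas, discomfort, and epistaxis". The section headed Data management and Safety Monitoring Plan opens with "All the data will be recorded anonymously using study subject number rather than personal identifiers" and continues with "OUHSC regulations regarding electronic information and data security will be followed". The only incident it requires to be reported is a data security incident.

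**The concern.** The plan puts safety into its rationale and lists the local harms it expects, then provides nowhere to write them down. The section whose title promises safety monitoring contains none. If staff follow the plan exactly, a nosebleed, a pressure injury, an unplanned admission or a decision to stop because the cannula was uncomfortable leaves no structured trace.

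Two things are at stake. First, the plan describes this as, to the authors' knowledge, the first outpatient study of HFNC effectiveness in COPD, and hopes it will lead to a larger randomised trial. That trial would inherit no rates of device-related harm and no reasons for discontinuation. Second, the sample size allows for 25% drop-out. Without a recorded reason, leaving because of intolerance cannot be told from any other loss, and that also bears on how the BCSS result in completers is read.

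**Working it through.** **The plan's own figure.** Statistical Analysis gives a difference of 1.3, a standard deviation of paired differences of 1.8, alpha 5% and power 90%, hence 22 patients, raised to 30 for 25% drop-out. Whether alpha is one- or two-sided is not stated.
- Two-sided normal approximation: (1.8 × (1.960 + 1.282) / 1.3)² = 20.1, so 21.
- Two-sided paired t-test, exact: power is 89.8% at 22 and 91.1% at 23.
- Drop-out: 22 / (1 − 0.25) = 29.3, so 30.

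The stated 22 and 30 reproduce within rounding. They are sized for BCSS alone, and no figure in the plan concerns harms.

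**Claim and named harms against planned data.**

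| Event of interest | Planned item that would record it |
|---|---|
| Facial or nasal injury, erythema, nosebleed, discomfort | None |
| Emergency visit, admission, death | None as such; a COPD-related event may appear in the exacerbation count |
| Stopping the device | Wear hours would show reduced or stopped use; the final question records whether the patient would keep it |
| Reason for stopping | None |
| Worsening of COPD | Exacerbation count, BCSS |
| Change in gas exchange | PaCO2 or bicarbonate, only if available |

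The helpfulness scale runs from no help to much help, so it has no harmful end.

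**What systematic recording could deliver.** If none of n exposed patients has a given event, the one-sided 95% upper limit for its rate is 1 − 0.05^(1/n).
- n = 22: 1 − 0.05^(1/22) = 12.7%.
- n = 30: 1 − 0.05^(1/30) = 9.5%.

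The upper end of a two-sided exact 95% interval is 1 − 0.025^(1/n): 15.4% for n = 22 and 11.6% for n = 30.

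The chance of seeing at least one event is 1 − (1 − p)^n. The documents give no rates, so p below is an assumption.

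| Assumed true rate p | n = 22 | n = 30 |
|---|---|---|
| 1% | 20% | 26% |
| 5% | 68% | 79% |
| 10% | 90% | 96% |

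**Which n applies.** Thirty is the enrolment target. Patients must complete a 3- or 4-month run-in and meet a compliance requirement before they receive the device, so the number exposed may be below 30. Twenty-two is the number required for the BCSS analysis. With 25% drop-out, 0.25 × 30 = 7.5, so seven or eight patients leave at some point, and the plan does not say how many do so before exposure.

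**The case against.** The strongest reply is that safety is a premise of the rationale and not an objective. The formal hypothesis concerns BCSS, and no safety analysis or conclusion is planned. This is correct. A reader might infer that the trial is set to declare HFNC safe merely because nobody asked. The documents do not support that, because they plan no such declaration.

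A reader might also infer that the trial gathers nothing relevant to harm and can neither support nor refute safety. That goes too far. Exacerbations are counted in both periods, BCSS is recorded several times a week, and PaCO2 or bicarbonate is compared where available. A marked deterioration in any of these would count against safety. Wear hours and the keep-or-return question give some view of tolerability. Nor are patients left without contact: there is a call or visit at 6-8 weeks on HFNC and a clinic visit at three months. The gap is that no safety question is specified for those contacts.

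Finally, about 30 patients cannot establish safety even with perfect recording, and since minor events are expected, zero events is a poor illustration for them. Both points stand. They limit what the data could show but do not remove the reason to collect them: common problems would probably be seen, and estimates with honest intervals are what a pilot can pass on.

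What remains is narrower but firm. None of the indirect items records the named local harms, serious events from any cause, or the reason for stopping, and with no concurrent control the indirect items cannot carry a conclusion of safety.

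**Conclusion.** The point holds as stated in the heading. It leaves the planned BCSS comparison and its sample size untouched. It is nevertheless more than a missing detail, because harms not asked about during follow-up cannot be reconstructed afterwards, and the remedy is cheap. It deserves correction before enrolment.

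In size: as written, no rate or bound can be given for any device-related harm. With systematic recording, zero events of one type would exclude, at one-sided 95% confidence, rates above about 12.7% if 22 patients are exposed. The 9.5% figure requires all 30 to start HFNC. Both assume that every exposed patient is asked.

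The conclusion rests on the protocol text. Title and consent pages were not available, and any institutional reporting duties outside the plan are not described in it.

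**What to change.** Add a one-page fixed checklist to contacts that already exist: the 6-8 week contact in each period, the fitting visit and the three-month visit.

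- **Both periods:** emergency visit, admission and death, each with its date.
- **HFNC period only:** nasal or facial injury, nosebleed, discomfort, and whether and why the device was stopped. A pre-device count of these is uninformative, since no cannula is worn.
- **Patients who leave:** record the date and reason, including for those who leave before receiving the device.

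Report the number of patients with each event with an exact 95% confidence interval. For device-related events the denominator is the patients who started HFNC. Give serious events by period with each period's own denominator and without a formal comparison: only patients who survive and comply with the run-in enter the second period, and those enrolled after an exacerbation have a longer first one. Label the table descriptive and not proof of safety.

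State these items under Data management and Safety Monitoring Plan, so that the section matches its title. Removing the safety wording from the rationale would cure the mismatch in the text but would leave harms unrecorded, so it is the weaker option.

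Cost: a few minutes per contact and one descriptive table. No added visits, tests or patients, and no change to treatment.

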## **Objectives**

The primary objective of this study is to look for a correlation between the use of HFNC in the outpatient setting in patients with previous COPD exacerbation and the change in their BCSS score. We hypothesize that home use of HFNC will lead to a reduction in BCSS score by 1.3.

Secondary objectives include; looking for a correlation between the use of home HFNC and COPD exacerbations in a 6 month period. COPD exacerbations are defined as worsening symptoms of COPD requiring a change in baseline medications/inhalers or a steroid or antibiotic prescription. No arterial blood gases will be performed as part of the study but we will look for PaCO2/serum bicarbonate change with the use of home HFNC, when possible.

## **Study Design and Methodology**

This is a prospective pilot study. Targeted population include patients with COPD, non-oxygen dependent, with a baseline normal bicarbonate on previous lab (within 6 months of enrollment). Patients will be randomly selected to be part of the study sample. Recruitment will occur in both inpatient and outpatient settings. An email briefly explaining the objectives of the study will be sent to Internal Medicine residents and Pulmonary Critical Care fellows to help in patients' recruitment. Patients will be enrolled in the study only after being seen by [name] or [name]. The study is expected to finish by the end of January 2017 or twelve months post IRB approval. Patients will be recruited and enrolled over six months, and the collected data will be analyzed six months after the last patient was included in the study. We will target a study sample of 30 as detailed in the statistical analysis section, where patients will be their own control (3 months without HFNC followed by 3 months with HFNC).

At the time of enrollment, demographic data, forced expiratory volume (FEV1) and a baseline PaCO2/serum bicarbonate when available will be collected. Patients will be taught how to calculate the BCSS score and will be provided with 120 photocopies of the BCSS score table (Table.1). They will be asked to complete the BCSS score every night if possible or at least 3 times per week. Patients will be followed for a total of 3 months, prior to starting home HFNC. Patients who were enrolled post COPD exacerbation will be followed for an extra month (a total of 4 months) and their BCSS scores from the first month will not be included in the statistical analysis since they will not be at their baseline at the time of enrollment. Compliance to follow up visits and completing the BCSS score will be a requirement to qualify for starting HFNC. To improve compliance, a follow up in the clinic or over the phone will take place at 6-8 weeks post enrollment.

After 3-4 months follow-up post enrollment, patients will be brought to the clinic for HFNC education/fitting. A baseline BCSS score (BCSS0) will be completed and the mean of last 3 months' BCSS scores ( $\overline{BCSS}_{w/oHFNC}$ ) will be calculated. The number of COPD exacerbation per last 3 months with new baseline PaCO2/serum bicarbonate, if available, will be collected. The HFNC device will be set at a fixed flow of 30L/min and a FiO2 of 21% (room air). Patients will be instructed to wear HFNC as long as they can while targeting at least 6 hours/day, and to record the number of hours they wear it per day. Patients will continue to complete the BCSS score every night or at least 3 times per week. After 6-8 weeks, a follow-up appointment over the phone or in the clinic will take place.

At the end of the 3 months HFNC trial, patients will be brought back to the clinic, and a BCSS score will be completed (BCSS3) and the mean BCSS of the last 3 months ( $\overline{BCSS}_{w/HFNC}$ ) will be calculated. The number of hours/day wearing the HFNC, the number of COPD exacerbations per last 3 months, and new baseline PaCO2/serum bicarbonate (if available), will be collected.

Both the difference between the mean of baseline BCSS scores ( $\overline{BCSS}_0$ ) and the mean of BCSS scores post 3 months HFNC ( $\overline{BCSS}_3$ ), ( $\Delta 0-3 \overline{BCSS}$ ); and the difference between the means of BCSS without HFNC ( $\mu_{\overline{BCSS}_{w/oHFNC}}$ ) and with HFNC ( $\mu_{\overline{BCSS}_{w/HFNC}}$ ), ( $\Delta \mu_{\overline{BCSS}_{w/oHFNC}} - \mu_{\overline{BCSS}_{w/HFNC}}$ ) will be calculated. The difference between the means of number of COPD

exacerbation per 3 months pre and post-HFNC, and the means of baseline PaCO2/serum bicarbonate (if available) pre and post-HFNC will be calculated as well, as secondary objectives. We will also look for a possible correlation between the number of hours using home HFNC and the change in BCSS score.

Regardless of the change/or not in BCSS score, patients will be able to provide their feedback regarding the device; they will be asked how helpful it was on a scale of 0 to 3, with 0 being equivalent to “not helpful at all” and 3 corresponding to “very helpful”. Patients will be asked as well if they would like to keep/not keep the device.

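### The analysis date, six months after the last inclusion, is one month short for patients enrolled post exacerbation, whose path takes 4 + 3 = 7 months

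*Combined protocol and SAP*

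**What the plan says.** All of the relevant text is in Study Design and Methodology.

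- **Accrual.** "Patients will be recruited and enrolled over six months".
- **Analysis date.** The timing is counted from the final entry into the study: "the collected data will be analyzed six months after the last patient was included in the study".
- **Overall duration.** "The study is expected to finish by the end of January 2017 or twelve months post IRB approval".
- **Default path.** Each patient is their own control, with three months without HFNC and then three months with it.
- **Second path.** "Patients who were enrolled post COPD exacerbation will be followed for an extra month (a total of 4 months"), with the first month's BCSS scores left out of the analysis. The description of the fitting visit allows for both paths: "After 3-4 months follow-up post enrollment, patients will be brought to the clinic for HFNC education/fitting".
- **End of follow-up.** "At the end of the 3 months HFNC trial, patients will be brought back to the clinic". BCSS<sub>3</sub>, the mean BCSS over the HFNC months, the hours of use and the on-HFNC exacerbation count are obtained at this visit. Until then, "Patients will continue to complete the BCSS score every night or at least 3 times per week".
- **Who may enter.** "Recruitment will occur in both inpatient and outpatient settings". Eligibility Criteria also requires an exacerbation in the past year and excludes patients who are still oxygen dependent after one, so entry soon after an exacerbation is foreseen.

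**The concern.** The analysis date appears to have been set from the default path alone. The longer path for patients enrolled post exacerbation is described in the same section, but the analysis date makes no allowance for it. No text bars such patients from entering late in recruitment, moves the analysis date for them, or says what happens to a patient whose HFNC period is still running on that date.

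BCSS<sub>3</sub> and the on-HFNC mean form one side of the primary BCSS comparison, and the on-HFNC exacerbation count is one side of a secondary comparison. All three depend on the end of the HFNC period. Followed to the letter, the plan would call for analysis before these values exist for some patients, in a study that aims for 30 patients and needs 22.

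**Working it through.** **Inputs (all from Study Design and Methodology)**

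- Recruitment period: 6 months.
- Analysis: last inclusion *L* plus 6 months.
- Time before HFNC: 3 months (default) or 4 months (enrolled post exacerbation).
- Time on HFNC: 3 months on either path.
- Diaries: nightly, or at least 3 per week.

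**Step 1. Reproduce the plan's figures.** The default path takes 3 + 3 = 6 months, which equals the stated lag with no slack. Recruitment plus lag is 6 + 6 = 12 months, which matches the expected duration if recruitment starts at IRB approval. The plan's figures therefore agree with each other for the default path.

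**Step 2. The longer path.** For patients enrolled post exacerbation the path takes 4 + 3 = 7 months. The extra month cannot be absorbed elsewhere: the first month is discarded, the other three pre-HFNC months supply the comparison mean, and the HFNC period is still three months. The shortfall is 7 − 6 = 1 month, about 30 days.

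**Step 3. Who is affected.** Let *E* be the enrolment date of a patient on the longer path and *x* = *L* − *E* in months. The end-of-HFNC visit is at *E* + 7 and the analysis at *L* + 6, so the visit is late by

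(*E* + 7) − (*L* + 6) = 1 − *x* months.

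This is positive only when *x* < 1. Patients on the longer path who enrol a month or more before the last inclusion finish in time, as does everyone on the default path.

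**Step 4. What would be outstanding on the stated date.** Three months is about 91 days or 13 weeks, giving 91 nightly diaries or 13 × 3 = 39 at the minimum frequency.

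| *x* (months) | Visit late by (months) | HFNC months completed | Nightly diaries outstanding | Diaries outstanding at 3 per week |
|---|---|---|---|---|
| 0 | 1 | 2 of 3 | about 30 of 91 | about 13 of 39 |
| 0.5 | 0.5 | 2.5 of 3 | about 15 of 91 | about 6.5 of 39 |
| 1 or more | 0 | 3 of 3 | 0 | 0 |

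**Step 5. How many patients.** The documents give neither the share enrolled post exacerbation nor the accrual pattern. As an illustration only, assume that 30 patients accrue evenly, so 30 / 6 = 5 enter in the last month. The expected number affected is then 5 times the assumed share: 0.5 at 10%, 1.25 at 25%, 2.5 at 50% and 5 at 100%. Dropout would lower these figures. The conclusion does not rest on them, and the true number may be zero.

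**Step 6. Total duration.** The longest path is 6 + 4 + 3 = 13 months against 12. This needs three conditions together: recruitment starts at IRB approval, it runs the full six months, and a post-exacerbation patient enters at its end.

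**The case against.** The strongest reply is that this sentence is a planning timeline. The duration beside it is only an expectation, with two alternatives. No text sets a data cut, a database lock or an analysis of incomplete patients, and the on-HFNC measures are defined at the end of the HFNC period, so the natural course is to wait until they exist. This largely stands. A reader might infer that the primary comparison will be run on truncated data or will be biased. The documents do not support that, because nothing in them requires the analysis to go ahead without the missing visits. The outstanding-diary counts show what a literal reading would imply; they are not a forecast.

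A reader might also infer that the twelve-month duration is shown to be wrong. It is not: the thirteen-month figure depends on the three conditions in the working, and the end-of-January-2017 alternative cannot be tested because no IRB approval date is given.

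It could also be argued that inclusion means the start of HFNC, in which case six months would be ample. This reading fits poorly. The same sentence speaks of enrolment over six months, and 6 + 6 gives the stated twelve. Counting from the start of HFNC would give 6 + 3 + 6 = 15 or 6 + 4 + 6 = 16 months.

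None of these replies removes the mismatch itself. The analysis lag is stated without qualification and is one month shorter than a path that the same section prescribes.

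**Conclusion.** The point holds as a minor inconsistency. The stated lag of six months covers the 3 + 3 month path only. Any patient enrolled post exacerbation less than one month before the last inclusion has the end-of-HFNC visit, and up to the last month of diaries, after the stated analysis date, by at most one month. This rests only on the plan's own durations and on reading inclusion as enrolment.

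The consequence is limited. The number affected cannot be derived and may be zero, and no data are lost if the analysis waits. The sample size is not called into question.

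**What to change.** In Study Design and Methodology, replace the fixed analysis date with a condition: the data will be analyzed after all enrolled patients have completed the end-of-HFNC visit or withdrawn, which may be up to seven months after the last enrolment. Patients who do not qualify to start HFNC should count as withdrawn for this purpose, since they will have no such visit. The condition should refer to all patients, because the last patient enrolled may be on the default path and finish before someone on the longer path who enrolled slightly earlier.

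Make the expected study duration consistent with this. A fixed thirteen months should not be written in as an upper bound, because that figure assumes that recruitment starts at IRB approval.

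The cost is at most one extra month before analysis. No visits, procedures or patients are added, and the follow-up and HFNC periods stay as written.
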